### 12.3. CURRENT SECURITY AND CONFIDENTIALITY STANDARDS

[figure not shown]
*For each database provided in Section 11.1, please Indicate the ability to be able to encrypt data access during transit (for example, accessed through an HTTPS connection); be able to encrypt data at rest (that is, when not in transit), have in place a data backup and recovery plan; require all users to have logins and passwords to access the data they are authorized to view; and have current anti-virus software installed to detect and address malware, such as viruses and worms.*

Database Name	Ability to encrypt	Ability to encrypt at rest?	Data Backup and Recovery Plan	Require all users to have logins	Current Anti-Virus Software Installed?

	data during transit?		Recovery Plan?	and passwords?	
nFORM	Yes	Yes	Yes	Yes	Yes
Qualtrics	Yes	Yes	Yes	Yes	Yes

**Figure 1: Theory of Change Logic Model for a Descriptive Study of the All In Dads! (AID) Project  
(target population is urban fathers who are 18+ years with children up to 24 years who are residents of Franklin County in Ohio)**

Unit of measurement is the individual participant.

## CONSORT Diagram for Action For Children: All In Dads!– Descriptive Evaluation

All in Dads! Healthy Marriage and Responsible
Fatherhood Program Evaluation

Statistical Analysis Plan

NCT05194020

October 17, 2024

1. Data Analysis

Briefly describe the planned approach for data analysis. If an impact analysis is proposed, name the key dependent and independent variables, and describe any methods to minimize Type I error (i.e., finding positive impacts by chance) such as limiting the number of impacts to be analyzed and/or multiple comparison correction. Describe proposed approach(es) for addressing missing data.

Identify study sample

The study sample includes participants who: 1) gave recorded informed consent to be part of the study, and 2) took both an entrance and exit survey (for attitudinal outcomes) or entrance and follow-up survey (for behavioral outcomes). The CONSORT diagram in Figure 2 shows exclusion criteria and the anticipated size of the overall study sample. The analytic sample for particular outcome measures will vary based on missing data.

Defining analysis measures

For each outcome construct, we have identified the relevant measures from nFORM that are theoretically aligned with that construct. We will generate a correlation matrix between items in a given construct to ensure that theoretically related items are also empirically related in our data set. Items that are not strongly correlated with other items in a construct will be removed as necessary. Factor analysis will be used to ensure that all construct items hang together (using an alpha of 0.7 or higher as the threshold). If an alpha of 0.7 cannot be obtained, that outcome will be removed.

Once we are confident that all of the items align with a given construct, we will create a composite measure by taking an average of the scores on each non-missing item in the construct. The measure definition matrix below provides information on each proposed outcome. For composite measures, a change score will be calculated between a participant's pre-program composite score and post-program composite score. For standalone survey items, a change score will be calculated between a participant's pre-survey and post-survey responses.

For the sake of consistency and simplicity, parenting and co-parenting analyses will use a participant's youngest child as the focal child.

Model Specification to Predict Outcomes With Dosage

Construct by Outcome	Dependent Variables (follow-up)	Response Codes for Dependent Variables	Dependent Variable Type	Independent Variables
Primary outcome:				
Parenting Behavior: 1 item	HOURSFU	# hours spent with child		Dosage: hours of attendance per service
	REACHFU	1 = Almost every day to 5 = never in past month	Continuous	

1 item 11 scaled items Co-parenting Behavior: 11 scaled items	ENGAGFU	1 = never to 5 = every day or almost every day	(using nFORM data); Co-variates: development starting points, risk - family structure, demographics, socioeconomic (ACS & OLLE survey data at baseline)
	COPARFU	1 = strongly disagree to 5 = strongly agree	
		1 = yes, 0 = no	

Secondary outcome:

Parenting Attitudes: 7 scaled items Financial Readiness 1 item 1 item	PATTFU	1 = always to 5 = never	Continuous	Dosage: hours of attendance per service (using nFORM data); Co-variates: development starting points, risk - family structure, demographics, socioeconomic (ACS & OLLE survey data at baseline)
	SAVFU			
	CHECKFU	1 = yes, 0 = no	Dichotomous	

Handling missing data

Outcomes

When creating the composite measures for co-parenting and parenting relationships, we will create a composite score by taking the average of multiple individual items. For these measures, our current plan is to use 20% as a threshold for allowable missing items, based on guidance from evaluation technical assistance resources. This plan is contingent on the final distribution of missing data in our data set. With a 20% threshold, if a respondent is missing more than 1 item used for creating the co-parenting construct or more than 2 items for creating the parenting construct, the respondent will be assigned a missing value for that construct. We will not be imputing truly missing values for outcomes. To create a construct score, the average will divide by the number of non-missing values in the construct.

Participants who have not seen their child within the past month will have their parenting behavior responses set to "Never" (1) and will be included in the analytic sample for that outcome.

For outcomes that use single survey items, participants who do not respond to the item on either the pre- or post-survey will be excluded from the analytic sample for that outcome.

Missing data for the implementation outcomes could happen as a result of programmatic data entry issues. For the sake of this evaluation, we assume that any primary or support services received by a participant are being accurately logged into nFORM, so a lack of documented attendance, service contacts, referrals, etc. is indicative of lack of services (i.e., a participant not receiving the program components as intended).

Assessing non-response bias

We will conduct response rate analysis for each primary outcome of interest to assess non-response bias and adjust for threats to internal validity. Using data from the Applicant Characteristics Survey, we will look at demographics (race, ethnicity, age, education level) and primary reason for joining the program among participants who fall into each of the following categories: 1) non-respondents who answered no surveys after the ACS, 2) respondents who completed the pre-survey only, 3) respondents who completed the post-survey only, and 4) respondents who completed both the pre- and post-survey (complete case).

Analytic approach

The main goal of this descriptive study is to assess pre-post change scores in the attitudinal outcomes listed above and assess pre-to-one-year follow-up change scores in the behavioral outcomes listed above among program participants before and after primary workshops. We will use paired sample t-tests to assess the magnitude and significance of changes among program participants in the analytic sample for each outcome. For binary economic stability outcomes, we will descriptively report the percent of participants who opened a checking or savings account one year after enrollment, compared to the percent who had opened these accounts before the program. We will adjust our p-values for multiple hypothesis testing and report the adjusted p-values in the appendix of the final report.

2. Data Archiving and Transfer

Briefly describe the planned approach data arching and transfer by addressing questions below.

What procedures and parameters are established for all aspects of data/information collection necessary to support archiving data collected as part of the evaluation?

Examples include informed consent, data maintenance, de-identifying data procedures.

All program data, including consent forms, service data, and surveys, will be maintained securely during the project period. Once the evaluation / research period is over, and data analysis and reporting are complete, MER will de-identify the data and make it available for sharing with other researchers or on federal data sites as appropriate. To facilitate this, MER has developed and will be implementing a data archiving plan for this project (as it does for all such major evaluation efforts). MER's Data Archiving plan/processes includes the steps of:

1. Inventorying and determining which data must be archived, and which data will not be archived or shared

	
(such as personally identifiable information of participants).
 
2. Ensuring that all required data elements are maintained in a way that is compliant with OFA and OPRE guidance and regulations and best practices. This includes the creation of supporting documentation such as a code book which makes the data useable by future researchers.
 
3. Developing an all-inclusive archive policy for the specific data needs, which ensures that archiving is achievable and manageable, and will include the specifics on the duration of data storage (5 years), benchmarks for archiving data, the variety of media to be used for storage – both Dropbox long term storage and physical storage on secured flash drives, and rules for who will have access to the data, including Dropbox controls and physical storage in a locked and fireproof storage facility.
 
4. Proactively protecting the data archive's integrity by selecting the Dropbox Enterprise company to warehouse the data and by using the protections described above, including the active scanning of stored data. Dropbox also includes search and discovery functions, automated back-up, and total encryption.

Describe how the collection methods for all types of proposed data collection will support the archiving and transfer of each type.
	
These systems support the data archiving function and facilitate the sharing of data, when appropriate, because the data collected will be combined from secure database systems and transformed into a tab delimited data sheet which can then be exported into a variety of formats including Excel.


How will consent form language represent plans to store data for sharing and/or transferring to other researchers?
	
The MER consent forms and processes clearly explain the use and long-term storage of data and the protection of personal and identifiable information to participants (and the de-identification of data kept long term).

Describe methods of data storage that will support archiving and/or transferring data.
	
MER's Data storage plan includes both physical and SAS (software as service) processes for long term storage and transfer. As the data set is being built, Qualtrics and Dropbox will be the primary and redundant systems for data storage. Once the all the data has been

	
collected and the dataset has been securely and completely de-identified, all data will be removed from Qualtrics and a long-term storage file with limited access will be maintained on Dropbox. In addition, physical download of the data will be made using multiple formats and copies (flash drive and CD or other media available at the time) and this data will be stored securely in two locked locations – a bank vault and MER headquarters protected in a safe behind multiple locks with limited access.
 
When transfer is appropriate, either a secure internet-based file transfer can be used, or a delivery of a physically stored data set can be done.

Explain how data and analyses file construction and documentation will support data archiving and/or transferring.
	
As part of the data analysis and cleanup process, a code book will be constructed that describes the data fields and how they were collected or constructed. Supporting documentation will be stored with the data sets for easy transfer when appropriate.

3. Dissemination

Briefly describe the planned dissemination efforts associated with the local evaluation, including any dissemination that will occur while the evaluation is ongoing (rather than after the evaluation is completed).

AFC and MER are planning on the publication and presentation of the findings of this research effort, both in a descriptive manner in the project's early years and regarding outcomes and impacts over time. MER will produce at least one manuscript for publication and make two professional presentations on the program and its findings. AFC and MER will use the most appropriate and robust analytical method possible in reporting results, including in the final report for the project to OFA, and to making the de-identified dataset available to the public after the conclusion of this project. In addition, we will make use of the HMRF network and conferences to share information with the field, and we will empower Action for Children to use evaluation findings in communications with other partners, funders, and their community.

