## EVALUATION PLAN

### 1. RESEARCH QUESTIONS

#### 1.1. OVERVIEW OF RESEARCH QUESTIONS

*Please state the research question(s) that the evaluation intends to answer and for each research question indicate the type: implementation or outcome.*

- *Implementation Questions: Identifying whether a program has been successful in attaining desired implementation goals (e.g., reaching intended target population, enrolling intended number of participants, delivering training and services in manner intended, etc.)*
- *Outcome Questions: Identifying whether program is associated with intended outcomes for participants (e.g., do participants' knowledge, attitudes, behaviors, or awareness change?)*

Research questions in this study are framed by a Descriptive Evaluation Design to assess whether outcomes improve for low-income fathers who participate in the All in Dads! (AID!) Project. Primary and secondary outcomes are assessed before and after participants complete core curricula—*Father Factor*, *The New Playbook*, and *Money Smart*—and *Job Readiness Coaching and Career Development* as employment support services (pre to post). Primary outcome measures will indicate whether behavior improved for healthy family relationships (parent, co-parent, and partner). Secondary outcome measures will indicate whether behavior improved for the attitudes and expectations that facilitate and reflect behavior for healthy family relationships and economic stability (financial, employment) (see Table 1 below).

No	Research Question	Implementation or Outcome?
R1	Will participants report significantly healthier parenting behavior one-year after completing primary educational services and employment support services?	Primary Outcome
R2	Will participants report significantly healthier co-parenting behavior one-year after completing primary educational services and employment support services?	Primary Outcome
R3	Will participants report significantly healthier financial behavior one-year after completing primary educational services and employment support services?	Secondary Outcome
R4	Will participants report significantly healthier parenting attitudes after completing primary educational services and employment support services?	Secondary Outcome

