## 1.2. OUTCOME RESEARCH QUESTIONS

For each outcome research question listed above, whether a descriptive or impact design, summarize the inputs (e.g., program components, program supports, implementation features, etc.), target population (e.g., the population for which the effect will be estimated) and the outcomes (e.g., child well-being, father-child engagement, etc.) that will be examined to answer the research question(s). Comparisons for descriptive evaluations may reflect circumstances before the grant, pre-treatment, or pre-determined benchmark from other studies with similar interventions.

Research Question Number Should correspond to the number indicated in Table 1.1 above	Intervention Program component or set of activities that the evaluation will test or examine	Target Population Population for which the effect of the treatment will be estimated	Comparison What the intervention will be compared to (e.g., pre-intervention for descriptive designs)	Outcome Changes that are expected to occur as a result of the intervention	Confirmatory or Exploratory? Confirmatory: those upon which conclusions will be drawn Exploratory: those that may provide additional suggestive evidence
R1	Primary curricula ( Father Factor, The New Playbook, and Money Smart ); Employment Support ( Job Readiness Coaching, Career Development ); Continuous Quality Improvement (CQI) Process	Low-income fathers who are 18+ years with children up to 24 years who are residents of Franklin County in Ohio	Assessment of healthy parenting behavior at AID! Project enrollment.	Participants who complete primary and support services will report healthier parenting behavior one year after AID! enrollment.	Confirmatory
R2	Primary curricula ( Father Factor, The New Playbook, and Money Smart ); Employment Support ( Job Readiness Coaching, Career Development );	Low-income fathers who are 18+ years with children up to 24 years who are residents of Franklin County in Ohio	Assessment of healthy co-parenting behavior at AID! Project enrollment.	Participants who complete primary and support services will report healthier co-parenting behavior one year	Confirmatory

	Continuous Quality Improvement (CQI) Process			after AID! enrollment.	

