## 9. DATA COLLECTION

### 9.1. CONSTRUCTS AND MEASURES

*Clearly articulate the constructs of interest, measures to evaluate those constructs, and specific data collection instruments. Provide any information on the reliability and validity of the data collection instruments. For standardized instruments, you may provide the citation for the instrument.*

Construct	Measure	Instrument	Reliability and Validity (if standardized instrument, you provide a citation for the instrument)
Parenting Behavior (interaction with children)	1 item: hours spent w/children in last 30 days (interval); 1 item: frequency reach out to children (categories, 5-point scale); 7 items: frequency engage in key behaviors (categories, 5-point scale)	nFORM Community-Based Fathers Survey (A2b, A2c, A5b: b-d, f-i)  *also asked on OLLE; will use data from survey with the most complete data	n/a

Co-Parenting Behavior	11 items: frequency of agreement with key co-parenting behaviors (interval, 5-point scale)	nFORM Community-Based Fathers Survey (A13: a-k)  *also asked on OLLE; will use data from survey with the most complete data	n/a
Father Financial Behavior	2 items: yes or no questions for have resume, checking/savings accounts (dichotomous)	nFORM Community-Based Fathers Survey (B3, B3a)  *also asked on OLLE; will use data from survey with the most complete data	n/a
Parenting Attitudes (toward children)	7 items: frequency of key attitudes (categories, 5-point scale)	nFORM Community-Based Fathers Survey (A3: a-g)  *also asked on OLLE; will use data from survey with the most complete data	n/a

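### The SAP's reliability rule can delete a confirmatory outcome: if alpha stays below 0.7, R2 (primary) or R4 has no planned result and no fallback

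*SAP*

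**What the plan says.** The SAP (Defining analysis measures) describes a sequence for every outcome construct. Inter-item correlations are inspected in the study data: "Items that are not strongly correlated with other items in a construct will be removed as necessary". The remaining items must then reach an alpha of at least 0.7, and the last step is "If an alpha of 0.7 cannot be obtained, that outcome will be removed". No correlation cut-off, minimum number of items or survey wave is given, and primary and confirmatory outcomes are not treated differently. The only significance test planned (SAP, Analytic approach) is a paired t-test per outcome.

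Protocol 1.2 labels R1 to R4 all confirmatory and glosses the label as "Confirmatory: those upon which conclusions will be drawn". Protocol 1.1 makes R1 and R2 primary. Protocol 9.1 lists 11 co-parenting items (A13 a to k) and 7 parenting-attitude items (A3 a to g), and enters reliability and validity as n/a for all four constructs.

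On missing items, the SAP (Handling missing data) says "our current plan is to use 20% as a threshold for allowable missing items". It then assigns a missing score to a respondent who is "missing more than 1 item used for creating the co-parenting construct or more than 2 items for creating the parenting construct".

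**The concern.** A reliability check on a composite is sound practice. The difficulty is what follows from failing it. Protocol 1.2 commits the evaluation to drawing conclusions on R2 and R4, while the SAP allows a property of the collected data to remove either one entirely. Low reliability is a reason to qualify a confirmatory result, not to leave the question unanswered. For R2 the stake is one of the two primary questions.

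A lesser issue remains if the outcome survives. Its item set may then be shorter than the one in protocol 9.1, chosen from the study data by a criterion the SAP does not state.

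The missing-item limits are a separate matter in the same part of the SAP. They decide which respondents receive a score, and they do not agree with the stated threshold.

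**Working it through.** **Which questions are exposed.** Set against protocol 9.1 and the SAP's model specification table:

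- R1: hours and reach-out are single items listed separately from the engagement scale, so R1 keeps a result if the scale is removed.
- R2: one 11-item composite (COPARFU), no other measure.
- R3: yes/no items, to which no scale alpha applies.
- R4: one 7-item composite (PATTFU), no other measure.

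Only R2 and R4 would be left with nothing.

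**How demanding 0.7 is.** The documents give no alpha to reproduce. For k items with mean inter-item correlation r, standardized alpha = k·r / (1 + (k − 1)·r). Setting alpha to 0.7 gives r = 0.7 / (0.3k + 0.7).

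- k = 11: 0.7 / 4.0 = 0.175
- k = 7: 0.7 / 2.8 = 0.25

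**Chance that the observed alpha falls below 0.7.** Inputs: n = 483 is the analytic sample in protocol 8.2; n = 338 is 483 × 0.70, the one-year response rate in protocol 9.5, in case 483 is really enrollment. For R4 the 90% post-program rate gives 483 × 0.90 ≈ 435, inside that range. The true alphas are assumptions. Items are taken as equally correlated and normal. By Feldt's result, (1 − α)/(1 − α̂) follows F with n − 1 and (n − 1)(k − 1) degrees of freedom, so P(α̂ < 0.7) = P(F < (1 − α)/0.3).

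| Assumed true alpha | 11 items, n = 338 / 483 | 7 items, n = 338 / 483 |
|---|---|---|
| 0.68 | 80% / 84% | 79% / 83% |
| 0.70 | 51% / 51% | 51% / 51% |
| 0.72 | 21% / 16% | 21% / 17% |
| 0.75 | 1.5% / 0.4% | 1.7% / 0.5% |
| 0.80 | 0% / 0% | 0% / 0% |

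These are values before pruning. Simulation with pruning added (an item is deleted only while that raises alpha) gives essentially the same figures, because with equally correlated items there is no weak item to drop.

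**Missing-item limits at 20%.**

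- Co-parenting: 11 items in both documents. 0.20 × 11 = 2.2, so 2 may be missing (2/11 = 18%). The SAP allows 1.
- Parenting engagement: protocol 9.1 gives 7 items, and 0.20 × 7 = 1.4 allows 1. The SAP table appears to give 11, and 0.20 × 11 = 2.2 allows 2. The SAP allows 2, which fits its own table but not protocol 9.1. That table's layout is broken in the text available, so the count of 11 is a probable reading only.

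**The case against.** The rule is stated in advance, and removal comes only after pruning has failed. Declining to test a scale that does not measure one thing is a respectable choice in a study the SAP calls descriptive. All of that stands, and it means the defect is the missing fallback, not the reliability check.

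The probabilities rest on assumed alphas, and equal correlations are the case in which pruning cannot help. That also stands. If instead 8 co-parenting items correlate at 0.28 and 3 are unrelated to them, alpha on all 11 items is 0.65 in the population, yet pruning recovers a usable 8-item scale and the simulated chance of removal is below 1% at either sample size. Nothing in the documents shows that an alpha near 0.7 is likely. Equally, with reliability entered as n/a, nothing shows that it will be comfortably exceeded.

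Three stronger readings are tempting. A reader might infer that a removed outcome would go unreported. The SAP is silent on reporting a removal, but a final report is planned and silence is not evidence of concealment. A reader might infer that the two missing-item limits were simply transposed. The SAP table, as it reads, lists 11 engagement items, which fits the parenting limit of 2, so exchanging the limits would move the inconsistency to parenting. A reader might also infer from the limit of 1 that the co-parenting scale has fewer than 11 items; both documents give 11.

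**Conclusion.** The point holds as a contingency. Followed as written, the SAP can leave R2 or R4 without a planned result, and it offers no substitute. R1 and R3 are not exposed in this way. The risk is material only if true alpha is below about 0.75: roughly even odds of removal at 0.70, 16 to 21% at 0.72, under 2% at 0.75 and effectively nil at 0.80. These figures assume equally correlated normal items and 338 to 483 respondents. The documents do not say where true alpha lies, so no single probability can be attached. The change is worth making because a confirmatory question is at stake and the remedy is cheap.

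The co-parenting missing-item limit is inconsistent with the SAP's own threshold whichever document supplies the item count. Whether the parenting limit is wrong cannot be settled until the engagement item count is.

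**What to change.** For confirmatory outcomes, replace the removal sentence with wording such as:

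> If alpha remains below 0.7, a confirmatory outcome will be kept. The composite on the full prespecified item set will be analysed and reported with its alpha and a reliability caveat. Any items dropped in pruning will be listed, and the full-item result will be reported alongside the pruned one.

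This keeps the reliability check and the pruning step, and does not require the full-item version to displace the pruned one when alpha is adequate.

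Separately, change the co-parenting limit so that 2 missing items are allowed, as 20% of 11 implies. Reconcile the engagement item count between protocol 9.1 and the SAP table, then set the parenting limit from it: 1 missing if there are 7 items, 2 if there are 11.

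The cost is SAP wording only, with no new data. The downside is that a composite of low reliability may be reported, with its alpha and caveat in view.

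### The R1 engagement scale has 7 items in the protocol and 11 in the SAP, and the SAP's missing-item limits for parenting and co-parenting do not follow from its 20% threshold

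*SAP*

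**What the plan says.** **Protocol, parenting behavior.** Section 9.1 defines the construct as two single items (hours with children, frequency of reaching out) plus an engagement set: "7 items: frequency engage in key behaviors (categories, 5-point scale". The instrument column identifies the items as "A2b, A2c, A5b: b-d, f-i". The data-collection table in 9.3 repeats the count of 7.

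**Protocol, co-parenting behavior.** Section 9.1 gives "11 items: frequency of agreement with key co-parenting behaviors (interval, 5-point scale".

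**SAP, model specification table (section 1, Data Analysis).** The primary-outcome rows name four variables, HOURSFU, REACHFU, ENGAGFU and COPARFU. The item counts run one item, then "1 item 11 scaled items Co-parenting Behavior: 11 scaled items". No item codes are given.

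**SAP, Handling missing data, Outcomes.** The threshold is introduced with "our current plan is to use 20% as a threshold for allowable missing items", and the SAP says that this depends on the final distribution of missing data. It is then turned into counts. A father's score is set to missing if he is "missing more than 1 item used for creating the co-parenting construct" or "more than 2 items for creating the parenting construct".

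**The concern.** Protocol 1.1 labels R1 and R2 primary outcomes, and 1.2 labels both confirmatory. Each composite is the mean of the non-missing items, so the item list determines the score, the change score and the fathers who can be analysed. As written, an analyst cannot tell from the two documents which items make up ENGAGFU. Nor can the analyst apply the missing-item rule to either scale without contradicting a stated count or the stated threshold.

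Timing adds to this. The SAP is dated October 17, 2024. The protocol timeline ends baseline collection on 3/31/2024 and post-test collection on 8/2/2024, with follow-up running to 5/31/2025. On that schedule much of the data was already in hand, so an unsettled item list leaves room for a choice made after looking at responses.

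**Working it through.** **Step 1: count the items.**
- Protocol engagement items: A5b b, c, d (3) plus f, g, h, i (4) = 7. The codes agree with the stated count in 9.1 and with 9.3.
- SAP engagement items: the four counts (1, 1, 11, 11) line up in order with HOURSFU, REACHFU, ENGAGFU and COPARFU. The first 11 stands before the co-parenting label, so it belongs to ENGAGFU.
- Co-parenting items: 11 in both documents.

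**Step 2: formulas.** For k items and a 20% threshold, the number allowed missing is m = floor(0.20 × k). The share missing is m/k.

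**Step 3: reproduce the SAP's own figures from its own counts.**
- Parenting, k = 11: floor(2.2) = 2, and 2/11 = 18.2%. The SAP's limit of 2 reproduces.
- Co-parenting, k = 11: floor(2.2) = 2. The SAP states 1, which is 1/11 = 9.1%. This does not reproduce.
- Rounding 2.2 to the nearest integer gives 2 and rounding up gives 3, in each case the same for both scales. No single rounding rule turns two 11-item scales into limits of 2 and 1.

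**Step 4: apply the limits to the protocol's counts.**

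| Scale | k | SAP limit | Share at SAP limit | Limit from 20% |
|---|---|---|---|---|
| Parenting, engagement items only | 7 | 2 | 2/7 = 28.6% | floor(1.4) = 1 |
| Parenting, plus one single item | 8 | 2 | 2/8 = 25.0% | floor(1.6) = 1 |
| Parenting, plus both single items | 9 | 2 | 2/9 = 22.2% | floor(1.8) = 1 |
| Co-parenting | 11 | 1 | 1/11 = 9.1% | floor(2.2) = 2 |

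The parenting limit exceeds 20% on every reading of the protocol's list. The co-parenting limit is stricter than 20% requires.

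**Step 5: which counts would fit the SAP's limits?** A limit of 1 corresponds to k = 5 to 9, and a limit of 2 to k = 10 to 14. The SAP's pair therefore implies 10 to 14 parenting items and 5 to 9 co-parenting items. The protocol has the reverse. With the limits exchanged (parenting 1, co-parenting 2), they match 7 and 11 exactly.

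**The case against.** **The SAP is consistent with itself on parenting.** This is true: 2/11 = 18.2% is under 20%. The excess appears only when the SAP's limit meets the protocol's 7 items. The co-parenting limit, however, fails on the SAP's own count.

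**The 20% threshold is provisional.** The SAP says so. That softens the threshold, but one provisional percentage still cannot give two different limits for two scales of equal length, and it does not settle which items are scored.

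**The table is damaged in extraction.** Assigning the first 11 to ENGAGFU is an inference from order. It is a secure one, because four counts match four variables and the count appears on both sides of the co-parenting label.

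**The SAP's item screening changes the list anyway.** It can remove weakly correlated items, so agreeing on 7 or 11 does not fully fix the scored list. This stands. But screening cannot take 7 items up to 11. It could bring co-parenting down to 9 or fewer, where a limit of 1 would fit, but the SAP does not say that its limit anticipates this.

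**The reach is limited.** ENGAGFU is one of three R1 variables, and the hours and reach-out items are single items in both documents. No item-missingness figure is given, so the number of fathers affected cannot be stated.

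**Stronger readings that the documents do not support.** A reader might infer that the sponsor intends two different parenting measures, or that four further items were added without a source. The SAP lists no codes, so no extra items can be identified or shown to exist, and the fit after swapping the limits points more towards a copying slip. A reader might also infer that the item count decides whether the scale passes the SAP's 0.7 alpha rule. No inter-item correlations are given, and screening comes first, so that cannot be shown.

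**Conclusion.** The inconsistency holds, in two linked parts. First, the engagement scale for a primary, confirmatory outcome has 7 coded items in the protocol and 11 uncoded items in the SAP. Second, the SAP's limits of 2 (parenting) and 1 (co-parenting) do not both follow from 20%: 2 missing is 28.6% of the protocol's 7 parenting items (22.2% at the least), while 1 missing is only 9.1% of the 11 co-parenting items, where 2 would be allowed.

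The likeliest explanation is an item count copied from the co-parenting row together with transposed limits. That is suggested by the exact match after swapping, not proved. The conclusion rests on reading the damaged SAP table in order and on rounding the 20% threshold down. The effect on the R1 and R2 estimates cannot be sized from the documents.

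**What to change.** Before analysis, state one item list for ENGAGFU in both documents.

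- **Default:** use the protocol's 7 items (A5b b-d, f-i), since only these are identified. Correct the SAP table to 7 with their codes. Set the score to missing if more than 1 parenting item or more than 2 co-parenting items are missing.
- **If 11 parenting items are truly intended:** list their codes in Protocol 9.1 and 9.3, and use more than 2 as the cut-off for both scales.

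Correcting the parenting limit alone would leave the co-parenting limit at odds with the threshold, so both belong in the same edit.

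The cost is wording in the SAP, and in the protocol only if 11 is kept. Under the default, a few fathers with 2 missing parenting items drop out of that composite, and some with 2 missing co-parenting items are kept.
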